### **7.3. Investigator/Sponsor Suspension or Termination of Patient Enrollment**

If, in the opinion of the Investigator, the clinical observations in the study suggest that it may be unwise to continue, the Investigator may suspend or terminate the study after consultation with the Sponsor (or designee). A written statement fully documenting the reasons for such a termination will be provided to the Sponsor (or designee) and the Institutional Review Board (IRB) or Independent Ethics Committee (IEC).

The Sponsor has the right to terminate the study or to close a site and remove all study materials from the clinical site. A written statement will be provided to the Investigator, the IRB or IEC, and regulatory authorities, if required.

Possible reasons for termination of the study at a clinical site include, but are not limited to:

- Unsatisfactory enrollment with respect to quantity or quality
- Inaccurate or incomplete data collection on a chronic basis
- Falsification of records
- Failure to adhere to the protocol
- Lack of study oversight by the Principal Investigator and/or designee

If any serious or nonserious AEs have occurred at such a clinical site, all documentation relating to the event(s) must be obtained.

## 8. TREATMENT OF PATIENTS

### 8.1. Description of Investigational Medicinal Product

Table 2: Investigational Medicinal Products

Product Name:	Bempedoic acid	Placebo to Match Bempedoic Acid
Dosage Form:	Film-coated tablets	Film-coated tablets
Unit Dose:	180 mg	Not applicable
Container/Closurea	35-count bottle with screw on childproof cap	35-count bottle with screw on childproof cap
Route of Administration:	Oral, daily at approximately the same time, with or without food	Oral, daily at approximately the same time, with or without food
Physical Description:		
Manufacturer (Fill/Finish):		

Study drug should be taken once a day (once every 24 hours) at approximately the same time every day and may be taken with or without food. Patients will fast for a minimum of 10 hours prior to collection of all laboratory samples.

Please see Pharmacy Manual for detailed storage requirements and instructions.

### 8.2. Concomitant Medications

Patients will be questioned about their concomitant medication use at each clinic visit. All concomitant medication taken chronically or intermittently during the study must be recorded with indication, total daily dose, and start and stop dates of administration.

The Prior/Concomitant electronic case report form (eCRF) will be used to record medications, herbal remedies, vitamins, other supplements, and over-the-counter medications taken within 3 months prior to screening and during the study.

### **8.2.1. Prohibited Lipid-Regulating Medications and Dietary Supplements**

- Patients will be required to stop taking all prescription or nonprescription drugs or dietary supplements taken for the purpose of lipid regulation at Month -4.5. With the exception of the study provided PCSK9i (Repatha 420 mg QM), no other lipid-modifying therapies or supplements will be permitted.

### **8.2.2. Allowable Medications**

- Hormone replacement (if stable 6 weeks prior to Month -4.5)
- Thyroid replacement (if stable 6 weeks prior to Month -4.5)
- Obesity medication (if stable 3 months prior to Month -4.5)

### **8.3. Blinding**

Patients who satisfy all entry criteria during the screening phase and complete the PCSK9i run-in period will be randomized to a treatment group at Day 1 (Visit T1). The Investigator or designee will contact IWRS at this visit to randomize the patient into the study. The IWRS will determine the randomized treatment assignment number and the appropriate study drug container via medication identification numbers (MED ID). A patient is considered to be randomized when they have been assigned a MED ID number by IWRS.

After patients have been randomized, study drug, which is assigned by the IWRS, will be administered in a double-blind fashion. The Sponsor, all clinical site personnel (Investigator, pharmacist, etc), and other vendor personnel will be blinded to the treatment group for each patient. Patients will also be blinded to the treatment they receive. Unblinded User(s) will be designated for each clinical site and at the sponsor (or designee) as needed. Unblinded individuals will be provided IWRS access allowing them the ability to perform emergency unblinding of treatment for an individual patient. An affirmative entry of the user's login details will be required before the treatment group is displayed. Unblinding at the clinical site for any other reason will be considered a protocol deviation. Unblinded treatments for patients will NOT automatically discontinue the patient from the study. To discontinue the patient from the study, the appropriate clinical site personnel will need to register the 'discontinuation' visit separately.

Blinding of treatment must be maintained for all patients unless, in the opinion of the Investigator, the safety of the patient may be at risk. Only under the rarest of circumstances should the Investigator consider breaking the blind and only when medical/supportive care cannot be provided without determining if the patient is receiving active drug treatment. In the event that the blind needs to be broken prior to completion of the study, the Investigator should contact the appropriate Medical Monitor by telephone. If the blind must be broken prior to consultation with the Medical Monitor, contact must be made within 24 hours of breaking the blind. At the initiation of the study, the clinical site will be instructed on procedures for breaking the blind via the IWRS. In all cases of breaking the blind, the Investigator must document in the patient's medical record the date, time, and reason for breaking the blind, and the names of personnel involved.

Limited vendors (ie, the bioanalytical laboratory and other vendor personnel, if any, that are responsible for PK analysis) will have access to the randomization codes to facilitate PK analytical work, and will be instructed to not communicate in any manner information associated with treatment assignment to any personnel at the clinical site, the Sponsor, or contract research organization (CRO).

Post-randomization values for individual laboratory measures for LDL-C, [REDACTED] TC, [REDACTED] non-HDL, ApoB, [REDACTED] and hs-CRP, including any plasma concentration of bempedoic acid and its metabolite that may inadvertently suggest treatment assignment will not be available to personnel from the clinical site, the patient, the Sponsor, and CRO.

An independent DMC will monitor unblinded accumulating patient safety and efficacy data until the last patient has completed study treatment. In addition, data on SAEs and deaths will be monitored by the DMC during this period. At each DMC review, relevant unblinded safety and efficacy information from ongoing studies will be provided to the DMC by an independent, unblinded [REDACTED] programmer and statistician. Additional details will be provided in a DMC Charter.

#### **8.4. Overdose**

There is no specific antidote for an overdose of bempedoic acid. Management of an overdose should be focused on the treatment of symptoms. These symptoms should be managed according to current standards of care with appropriate supportive measures. Also discontinuation of study drug should be considered, based on medical judgement.

## **9. INVESTIGATIONAL MEDICINAL PRODUCT**

### **9.1. Investigational Medicinal Product Supply and Control**

The Sponsor will supply the investigational medicinal product (IMP) for this study. The IMP for this study includes bempedoic acid (180-mg film-coated tablets) and matching placebo (film-coated tablets). IMP will be distributed and released in accordance with regional and local requirements during the conduct of the study.

PCSK9i will be provided as background therapy. This will be dispensed and administered during clinic visits and will be stored and taken as commercially labeled.

The MED ID number (an identifier on the study drug packaging) will be obtained via IWRs and used to select PCSK9i and double-blind IMP for the treatment period from available clinical supplies at the clinical site.

Double-blind IMP will be dispensed in 35-day supply increments to patients by appropriate clinical site personnel. Patients will receive one 35-day supply bottle at Day 1 (Visit T1) and at Month 1 (Visit T2).

Please see Pharmacy Manual for detailed storage requirements and management instructions.

### **9.2. Administration of Investigational Medicinal Product**

Patients will be instructed to ingest IMP starting at Visit T1 for the duration of treatment period orally once daily (once every 24 hours) at approximately the same time each day with water. IMP may be taken with or without food. On clinic visit days, patients will be instructed to delay ingestion of IMP until all study procedures have been completed. If a patient arrives at clinic on Visits T1, T2, or T3 without having fasted or having taken IMP before arriving at the clinic, reschedule the visit (the next day or as soon as possible) so that the fasting and dosing requirements have been met. Patients will be instructed to return all packaging and unused IMP at each clinic visit.

If the patient forgets to take IMP at the usual time on nonclinic visit days, it may be taken up to 12 hours later the same day. After that time, the patient should not take IMP that day and should resume ingestion of IMP the following day. If a patient fails to take IMP, details describing the reasons for nondosing should be documented in the patient's medical records and eCRF. Extra IMP (7 extra days per bottle) is provided and can be used, if needed, prior to the next visit or to replace a dose of IMP that cannot be used because it is lost or damaged.

PCSK9i will be administered on site at Visits S2, S3, S4, T1, and T2. Doses will be stored and administered as required in prescribing information

### **9.3. Investigational Medicinal Product Accountability**

Accurate records of the receipt of all IMP and PCSK9i shipped by the Sponsor (or designee) and the disposition of the IMP and PCSK9 must be maintained.

IMP records or logs must comply with applicable regulations, local law, and guidelines, and should include:

- Amount received/placed in storage area
- Amount currently in storage area
- MED ID number for all IMP
- Dates and initials of person(s) responsible for IMP/PCSK9i inventory (including entry/movement/disposition)
- Date and amount of IMP/PCSK9i dispensed to each patient, including unique patient identifiers
- Date that IMP/PCSK9i was returned by patient, assessment of compliance, and relevant documentation of discrepancies
- Nonstudy disposition (eg, lost, broken, wasted)
- Amount returned to Sponsor/Sponsor's designee/destroyed or amount destroyed per local standard operating procedure (SOP) following accountability by site monitor.

### **9.4. Investigational Medicinal Product Handling and Disposal**

Upon completion or termination of the study, all used and unused IMP with the IMP packaging must be returned to the Sponsor (or designee) for eventual destruction unless otherwise authorized by the Sponsor. All IMP returns must be accompanied by the appropriate documentation.

## 10. STUDY PROCEDURES

### 10.1. Informed Consent

The patient must be adequately informed of the nature and risks of the study and understand the informed consent document (ICD). No study-related procedure will be performed until the patient has been completely informed of the study, has freely consented to take part in the study, and has signed and dated an ICD approved by the Sponsor (or designee) and the IRB or IEC.

### 10.2. Procedures and Schedule of Assessments

Patients who provide informed consent and sign the ICD will be eligible to begin screening for the study. The study is comprised of 3 distinct periods: screening, PCSK9i run-in and double-blind treatment.

The schedule of study events is provided in [Appendix 1](#). However, a patient can be seen at any time for reasons of safety.

Data will be captured on eCRFs. Randomization, drug supply (re)ordering, and patient tracking will occur via IWRS. Instructions for these systems will be provided separately.

#### 10.2.1. Screening Month -4.5 (Visit S1)

The screening period will begin with a screening visit that will occur approximately 18 weeks prior to randomization. Visit S1 will allow the Investigator to assess the patient's preliminary eligibility. After the patient provides written informed consent (see [Section 10.1](#)), the patient will undergo the following assessments and procedures at Visit S1:

- Demographics
- Clinically relevant medical history
- Concomitant and prohibited medication review
- Height (cm), weight (kg), body mass index (BMI)
- Vital signs
- Clinical laboratory evaluations:
  - Hematology, blood chemistry, and urinalysis
  - Basic fasting lipids (TC, calculated LDL-C, [REDACTED], non-HDL-C, [REDACTED], and [REDACTED])
  - HbA1C
  - TSH
  - FSH (in appropriate female patients)
  - Serum pregnancy test (on appropriate female patients)
- Serology (including HBsAg, Hepatitis C virus [HCV])

- Review of all inclusion/exclusion criteria that can be assessed at this time
- Conduct diet and exercise counseling
- Contact IWRS to register the patient

Patients who meet all enrollment criteria that can be assessed following review of the S1 central clinical laboratory results (available several days after Visit S1) will be instructed to washout of all lipid-regulating drugs and supplements and to maintain consistent diet and exercise patterns throughout the study. Patients who fail to meet any entry criterion that can be assessed at Visit S1 are considered to be screen failures and are not required to return for additional visits (although a patient can be seen at any time for safety reasons).

#### **10.2.2. PCSK9i Run-in Month -3 (Visit S2)**

Prior to scheduling Visit S2, review the screening clinical results to evaluate whether the patient continues to meet eligibility criteria.

- If the patient meets eligibility criteria, then schedule the Visit S2 and proceed with the Visit S2 procedures

The patient will undergo the following assessments and procedures at (Visit S2)

- Concomitant and prohibited medication review (ongoing)
- Assess AEs (starting from signing of the informed consent document)
- Physical examination (PE)
- Vital signs
- Basic fasting lipids (TC, calculated LDL-C, [REDACTED], non-HDL-C, [REDACTED], and [REDACTED])
- ApoB and hs-CRP
- First PCSK9i monthly injection. Verification of lipid entry criteria (LDL-C value of >160 mg/dL and triglycerides <500 mg/dL) must be obtained before starting PCSK9i
- Schedule next visit **(S3 has to be at least 30 days ± 3 days from the first dose of PCSK9)**
  - PCSK9i injections must be administered consistently throughout the trial within 30 ± 3 days from the previous dose. Efficacy will vary if the doses are not consistently administered.

Note: Local labs can be used to assess LDL-C and TGs for entry. All other labs must be run via the central lab. If using a central lab or a local lab with a delay in obtaining results, an optional visit to administer PCSK9 may be scheduled. **Patients need to be on Repatha 420 mg for at least 30 days ± 3 days before conducting Visit S3.**

### 10.2.3. PCSK9i Run-in Month -2 (Visit S3)

Prior to scheduling Visit S3, review the screening clinical results to evaluate whether the patient continues to meet eligibility criteria.

- If the patient continues to meet eligibility criteria, then schedule Visit S3 and proceed with Visit S3 procedures

The patient will undergo the following assessments and procedures at (Visit S3)

- Concomitant and prohibited medication review (ongoing)
- Assess AEs (starting from signing of the informed consent document)
- Vital signs
- Basic fasting lipids (TC, calculated LDL C, [REDACTED] non-HDL C, [REDACTED], and [REDACTED])
- PCSK9i monthly injection must be given at the end of procedures

### 10.2.4. PCSK9 Run-in Month -1 (Visit S4)

One month ( $30 \pm 3$  days) from S3, patients will have their LDL-C evaluated a second time via **central lab only** prior to randomization on Day 1.

The patient will undergo the following assessments and procedures at (Visit S4)

- Concomitant and prohibited medication review (ongoing)
- Assess AEs (starting from signing of the informed consent document)
- Vital signs
- Basic fasting lipids (TC, calculated LDL C, [REDACTED], non-HDL C, [REDACTED], and [REDACTED])
- Schedule next visit Day 1 **(Day 1 should occur  $30 \pm 3$  days after S4, once LDL-C eligibility  $\geq 70$  mg/dL is established)**
- PCSK9i monthly injection must be given at the end of procedures

### 10.2.5. Treatment Week 0 (Visit T1; Day 1)

Prior to scheduling Visit T1, review S1, S2, S3, and S4 clinical results to evaluate whether the patient continues to meet eligibility criteria.

- If the patient meets eligibility criteria, then schedule the Visit T1 and proceed with the Visit T1 procedures

If the patient has met all inclusion criteria, none of the exclusion criteria, and has been on Repatha 420 mg **for  $30 \pm 3$  days during each month of the PCSK9 run-in period**, the patient may be randomized into the double-blind treatment period. Patients who fail to meet any entry criterion prior to randomization are considered to be screen failures, will not be randomized into a treatment group, and are not required to return for additional visits. Patients are considered randomized once all eligibility criteria are confirmed and a randomization number is obtained by the IWRs on the day of first dose.

The patient will undergo the following assessments and procedures at (Visit T1)

- Concomitant and prohibited medication review (ongoing)
- Assess AEs (starting from signing of the informed consent document)
- Weight
- Vital signs
- Clinical laboratory evaluations:
  - Hematology, blood chemistry, and urinalysis

Note: Urine pregnancy test (for females of childbearing potential)

- Basic fasting lipids (TC, calculated LDL-C, [REDACTED], non-HDL-C, [REDACTED], and [REDACTED])
- ApoB and hs-CRP
- HbA1C

- Predose PK
- Review inclusion/exclusion criteria to establish patient eligibility. **Patient must have an LDL-C  $\geq 70$  mg/dL at S4 before they can be randomized on Day 1.**
- Conduct diet and exercise counseling
- IWRS contact to obtain the patient randomization number and MED ID number for double-blind study drug
- Dispense IMP and provide dosing instructions (35-day supply bottles)
  - **Subject should be randomized and receive IMP within  $30 \pm 3$  days of S4, as soon as the final LDL-C entry criterion is met**
- PCSK9i injection and IMP must be given at the end of procedures
- Schedule next visit

#### 10.2.6. Treatment Month 1 (Visit T2 $\pm 3$ days)

If the patient is withdrawing early from the study at this visit, proceed to [Section 10.3.2](#) for the list of the required assessments.

If the patient is withdrawing from IMP treatment at this visit, proceed to [Section 10.3.2](#) for the list of the required assessments.

Patients will undergo the following assessments and procedures at Month 1 (Visit T2):

- Concomitant and prohibited medication review (ongoing)
- Assess AEs since last visit (ongoing)
- Vital signs
- Clinical laboratory evaluations:
  - Hematology, blood chemistry, and urinalysis

- Basic fasting lipids (TC, calculated LDL-C, [REDACTED], non-HDL-C, [REDACTED], and [REDACTED])
- ApoB and hs-CRP
- Predose PK. Should be taken ideally within 4 hours of the patient's normal time of dosing
- Conduct diet and exercise counseling
- Return of IMP; assessment and recording of IMP compliance
- Dispense IMP and provide dosing instructions (35-day supply bottles)
- PCSK9i injection and IMP must be given at the end of procedures
- Schedule next visit

#### **10.2.7. Treatment Month 2 (Visit T3 ±3 days)/EOS**

If the patient is withdrawing early from the study at this visit, proceed to [Section 10.3.2](#) for the list of the required assessments.

If the patient is withdrawing from IMP treatment at this visit, proceed to [Section 10.3.2](#) for the list of the required assessments.

Patients will undergo the following assessments and procedures at Month 2 (Visit T3):

- Concomitant and prohibited medication review (ongoing)
- Assess AEs since last visit (ongoing)
- PE
- Weight
- Vital signs
- Clinical laboratory evaluations:
  - Hematology, blood chemistry, and urinalysis
  - Basic fasting lipids (TC, calculated LDL-C, [REDACTED], non-HDL-C, [REDACTED], and [REDACTED])
  - ApoB and hs-CRP
  - HbA1C
- Predose PK. Should be taken ideally within 4 hours of the patient's normal time of dosing
- Conduct diet and exercise counseling
- Return of IMP; assessment and recording of IMP compliance
- Complete study status in IWRS (ie, completed study).

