TC	Total cholesterol
TEAE	Treatment-emergent adverse event
TG	Triglycerides
TSH	Thyroid-stimulating hormone
ULN	Upper limit of normal
WBC	White blood cell
WHO	World Health Organization

2 Introduction

The purpose of this document is to describe the statistical methods, data derivations and data summaries to be employed in ETC-1002-039. The preparation of this statistical analysis plan (SAP) has been based on International Conference on Harmonisation (ICH) E3 and E9 Guidelines and in reference to Protocol 1002-039 (Protocol Amendment 1, March 05, 2017).

The SAP will supersede the protocol in the event of any differences between the two documents in the plans for data analysis, and the protocol will be amended if appropriate. The SAP will be included as an appendix in the clinical study report for this protocol.

3 Study Objectives and Endpoints

[figure not shown]

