5.1 General Statistical Considerations

Summary statistics for continuous variables will include the number of patients, mean, median, standard deviation or standard error, minimum, and maximum. Minimum and maximum will be presented same number of decimal places as reported/collected, one additional decimal place for mean and median, and two additional decimal places for SD.

For categorical variables, the frequency and percentage will be given. Percentage will be presented with one decimal place. All categories will be presented (even if no patients are counted in the category). Counts of zero in any category will be presented without percentage.

Data will be presented on listings in order of patient, assessment date and assessment (in order collected on CRF, unless specified otherwise). Dates will be presented in format DDMMYY YYYY.

The visit schedules and window are shown below.

Visit	S1	S2	S3	S4	T1	T2	T3, EOS
Slotted Study Month	Month -4.5	Month -3	Month -2	Month -1	Week 0	Month 1	Month 2
Target Study Day	NA	Day of first 420mg PCSK9i injection	Day of 420mg PCSK9i injection during S3	Day of 420mg PCSK9i injection during S4	Day 1	Day 31	Day 61
Analysis Visit Windows	NA	within 21 days prior to 420mg PCSK9i injection	420mg PCSK9i injection during S3 visit \pm 3 days	420mg PCSK9i injection during S4 visit \pm 3 days	PCSK9i injection (regardless dose) during T1 visit \pm 3 days	T1 injection of PCSK9i (regardless dose) + 30 \pm 3 days	T2 injection of PCSK9i (regardless dose) + 30 \pm 3 days
Protocol Defined Visit Window	-135	-90 \pm 3	-60 \pm 3	-30 \pm 3	1	31 \pm 3	61 \pm 3

The details of visit window derivations will be described on the programming specifications.

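### T3 is dated from Day 1 in the protocol but from the T2 Repatha injection in the SAP, so a compliant Month 2 LDL-C sample can fall outside the SAP analysis window

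*Protocol*

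**What the plan says.** **Visit days.** Section 10.2.7 of the protocol is headed "Treatment Month 2 (Visit T3 ±3 days)/EOS". The target days are in the Schedule of Events (Appendix 1 of both documents): T2 at Day 31 ±3 and T3 at Day 61 ±3, both counted from Day 1.

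**Injections.** Section 9.2 states: "PCSK9i will be administered on site at Visits S2, S3, S4, T1, and T2". T3 has no injection. The protocol's rule that doses be 30 ±3 days apart therefore fixes T1 to T2 but does not reach T3.

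**Booking instructions.** At S2 the site is told that "S3 has to be at least 30 days ± 3 days from the first dose of PCSK9". At S4 the line "Schedule next visit Day 1" is followed by an interval of 30 ±3 days. At T2 (Section 10.2.6) the line is only "Schedule next visit". T1 has the same bare line, but there the dosing rule supplies the interval.

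**Analysis window.** In the visit table of SAP 5.1, the analysis window for Month 2 is "T2 injection of PCSK9i (regardless dose) + 30" ±3 days. The row beneath prints the protocol window, 61 ±3. The table is followed by: "The details of visit window derivations will be described on the programming specifications". SAP Section 2 adds: "The SAP will supersede the protocol in the event of any differences between the two documents in the plans for data analysis".

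**Analysis set and missing values.** SAP 5.2.1.2 makes Repatha 420 mg within 30 ±3 days before the lipid measurement a condition of the mITT set. SAP 5.3.1 fills a missing Month 2 LDL-C with the last post-baseline observation and adds an analysis of observed data only. The list of changes from the protocol in SAP Section 6 does not mention the Month 2 window.

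**The concern.** Month 2 LDL-C is the primary endpoint, and the two documents time its sample from different starting points. A patient can attend T2 and T3 on permitted days and still give a sample that the SAP window does not accept.

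If that happens, the value leaves the observed-data analysis. In the primary analysis two outcomes are possible. LOCF may put the Month 1 value in its place, or the T3 value may itself count as the last post-baseline observation, which leaves the result unchanged. The SAP text does not say which. That choice affects which primary-endpoint values are analysed, and it should not be left to a programming document outside the SAP.

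**Working it through.** **Inputs**
- T2 on Day 28 to 34 and T3 on Day 58 to 64 (Appendix 1).
- Repatha given at the T2 visit, so injection day = T2 day (protocol 9.2 and 10.2.6).
- SAP Month 2 window: 27 to 33 days after the T2 injection (SAP 5.1).
- 26 patients planned per arm (SAP 4.3).

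**Step 1: reproduce the target days.** Day 1 + 30 = Day 31, and Day 31 + 30 = Day 61. Both match SAP 5.1, so the documents agree when every visit is on target.

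**Step 2: Month 1.** T2 on Day 28 to 34 is 27 to 33 days after Day 1. None of the 7 T2 days falls outside the SAP window.

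**Step 3: Month 2.** Write T2 = 31 + a and T3 = 61 + b, with a and b from −3 to +3. The lag is T3 − T2 = 30 + b − a, which runs from 24 to 36 days over 7 × 7 = 49 pairs. Pairs outside 27 to 33:

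| Lag (days) | 24 | 25 | 26 | 34 | 35 | 36 |
|---|---|---|---|---|---|---|
| Pairs | 1 | 2 | 3 | 3 | 2 | 1 |

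The total is 12 of 49. One example is T2 on Day 28 with T3 on Day 62 (34 days); another is T2 on Day 34 with T3 on Day 60 (26 days).

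**Step 4: from schedules to patients.** The documents do not give the spread of visit dates, so the shares below are assumptions. Normal offsets are rounded to whole days and kept within ±3. Patients per arm = share × 26.

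| Assumed T2 and T3 offsets | Share outside | Per arm |
|---|---|---|
| T3 booked 27–33 days from the T2 injection | 0% | 0 |
| Normal, SD 1, correlation 0.5 | 0.1% | 0.0 |
| Normal, SD 1, independent | 1.5% | 0.4 |
| Normal, SD 1.5, correlation 0.5 | 1.7% | 0.4 |
| Normal, SD 1.5, independent | 7.9% | 2.1 |
| Triangular (weights 1,2,3,4,3,2,1), independent | 11.7% | 3.0 |

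**Step 5: effect on the estimate.** Suppose k of 26 patients per arm have Month 1 put in place of Month 2, and they are typical of their arm. The treatment difference then moves by k/26 of the gap between the Month 1 and Month 2 treatment effects. For k = 3 this is 3/26 = 0.115, or 12% of that gap. The documents do not give the gap. As an illustration, a gap of 5 percentage points would move the estimate by 5 × 0.115 = 0.6 points.

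**Step 6: is a joint rule workable?** T3 days that are both 27 to 33 days after T2 and within Day 58 to 64:

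| T2 day | 28 | 29 | 30 | 31 | 32 | 33 | 34 |
|---|---|---|---|---|---|---|---|
| T3 days | 58–61 | 58–62 | 58–63 | 58–64 | 59–64 | 60–64 | 61–64 |
| Count | 4 | 5 | 6 | 7 | 6 | 5 | 4 |

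The counts sum to 37 = 49 − 12. Tying T3 to the injection alone would not be enough: it allows T3 from Day 55 to Day 67, and 12 of those 49 pairs miss Day 61 ±3.

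**The case against.** **The SAP already indicates which window governs.** One row is labelled as the analysis window and the other as the protocol's window, and the SAP takes precedence for analysis. The natural reading is that the injection-based window governs, and 5.2.1.2 points the same way. Timing from the injection also looks deliberate, since the protocol warns that efficacy varies with inconsistent dosing. This stands, so it would be too strong to say that the SAP leaves the governing window wholly open. But it makes the mismatch matter more: if the injection window governs, a compliant T3 sample can fail it.

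**The loss is not certain.** The derivations sit in programming specifications that are not available, and one reading of LOCF leaves the primary result unchanged. The mITT condition is also ambiguous. If it applies to the patient, a compliant Month 1 sample can satisfy it; if it applies to each measurement, a sample at 34 to 36 days fails, and one at 24 to 26 days fails too if the interval is read as 27 to 33 days. So the documents support a possible loss, not a certain one.

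**12 of 49 looks large.** A reader might infer that about a quarter of patients are affected. That would need T2 and T3 days to be independent and uniform over their windows. T3 is booked at T2, so some dependence is plausible, and the two largest shares in the table both need independence.

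**No bias between arms.** A reader might infer that the mismatch favours one treatment. Treatment is blinded and post-randomization lipid results are masked, so nothing in the documents suggests that visit timing would differ by arm.

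**Conclusion.** The mismatch is in the text and the date arithmetic is exact: compliant visits allow a lag of 24 to 36 days, against a SAP window of 27 to 33. The effect on patients is an estimate. It is about 0 to 3 of 26 per arm, depending on the assumed spread of visit days and on how closely T3 follows the T2 date. At the top of that range, and only if Month 1 is substituted, the primary estimate would move by 12% of an unknown gap between the Month 1 and Month 2 effects.

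The expected effect is small, with no reason to think that it differs between arms. The documents do not support a claim of bias or of a material loss of power; the sample-size assumptions are redacted, so power cannot be checked. The case for acting is that following both documents as written can set aside a valid primary-endpoint measurement, and preventing this costs very little. It is a cheap improvement, not a threat to the trial's conclusion.

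**What to change.** **Protocol.** In the "Schedule next visit" line of 10.2.6, in 10.2.7, and in both copies of Appendix 1, require T3 to be 27 to 33 days after the T2 injection and within Day 61 ±3. This agrees with SAP 5.1 and 5.2.1.2 and is possible for every T2 day from 28 to 34.

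**SAP.** For visits already held and for later deviations, amend 5.1 and 5.2.1.2 together. State that a T3 LDL-C taken within Day 61 ±3 is mapped to Month 2, and that it is not excluded from the mITT analysis solely because the Repatha interval was 24–26 or 34–36 days. Add a sensitivity analysis that excludes those samples, and say there whether Month 1 is carried forward in their place. Changing 5.1 alone would leave it in conflict with the Repatha condition in 5.2.1.2.

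**Cost.** A scheduling sentence in the protocol and matching wording in two SAP sections. No visits, samples or patients are added. The booking window for T3 narrows from 7 days to between 4 and 7, depending on the T2 date.
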